While study results demonstrated many benefits of ePartogram use, additional needed software refinements were identified, and further research is needed to assess its use in a greater variety of clinical settings. The proposed ePartogram effectiveness aims to further test the ePartogram software and use of ePartogram on clinical decision-making and care.

[figure not shown]
III. Study Design

- A. Provide an overview of your **study design and methods**.

Study Design

The study design is a quasi-experimental design evaluation with labor management outcomes compared for the study period between two study groups, intervention and control. The study will involve mixed methods – quantitative and qualitative data. The study is depicted below.

Figure 1. Study Design and Phases

Methods

The study will be conducted in the following phases.

Phases

- 1) An initial group of **facilities selected** for participation will be confirmed in Kisumu County and Meru County. A rapid formative assessment of possible facilities collected data on:
 - a. training needs on the paper partograph and
 - b. supplies, drugs and equipment available in stock for monitoring of normal labor, management of complications and referrals (facility assessment tool; this will be repeated every 3 months) (?).
 - c. percent of births recorded in the register at the facility in past 3 months that had a partograph started and used.
 - d. this activity received a non-HSR determination.
- 2) In each region, we expect approximately 6 facilities to participate. Within each region, equal numbers of facilities that will be purposively assigned to the study groups. Each study group will have facilities that have a similar birth volume, staffing levels, and BEmONC/CEmONC status, as much as possible so the two group are similar
 - a. Kisumu District Hospital and Meru Teaching and Referral Hospital must be intervention sites and will not be randomly allocated to the study group.
- 3) We will seek **approvals**:
 - a. 2 IRB approvals (JHSPH and KEMRI in Kenya) (see section X.E of this document).
 - b. Ministry of Health Approval to work in their sites
 - c. County Approvals (Kisumu and Meru)
 - d. Facility in-charge agreement will be sought at time of provider enrollment.
- 4) A similar three-day **whole-site training** will be carried out in each participating health facility in both study groups on labor management and partograph use by providers following Kenyan and WHO guidelines.

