12) To answer the secondary research questions, starting in the second month after implementation, study manager will carry out **in-depth interviews** (or small focus group discussions) with providers at sites in both study groups. We will interview providers who use the paper partograph or the ePartogram to discuss barriers and facilitators to usage, including facility conditions. The supervision for providers around the ePartogram and paper-partograph use will also be explored. The interviews will be audio-recorded to capture all contributions from participants. Participants will be informed about this during consenting. The digital recorders erased/audio tapes will be destroyed after transcription and the recordings will not be used for any other purposes.

B. Provide a **sample size and a justification** as to how you arrived at that number. If you use screening procedures to arrive at a final sample a table may be helpful.

The third study objective deals with clinical actions for complications and requires the largest sample size due to the rarity of complications. We describe inputs to sample size as shown in Table 1.

Inputs to the sample size calculation are as follows:

- *Number of sites*: The available 12 sites (6 in each study arm) have 1342 births per month, , on average. So 6 facilities have 671 births per month. We believe 80% of these will have a partograph completed during the study.
- *Prevalence*: Kenya QoC report⁹ stated that “19% of labors crossed the partograph ‘action line’”. While this appears high, we also will look for labors with more than one abnormal measurement signaling an early complication. (A study by Orji et al in Nigeria in 2008 also found 18.5% of labors crossed the action line.) For our study, we use the 19% to indicate that up to 19% of labor may cross the action line OR may have 1+ abnormal measurement that signal need for provider action.
- *Average cluster size*: is calculated to be 17.6
- *Intraclass correlation*: ICC is expected to be high as the facilities are a heterogeneous mix of district hospitals, health centers and some private facilities, so we assume ICC of 0.15.
- *Coefficient of variation*: COV is assumed to be 90%, after calculating the standard deviation of the average monthly births in these sites. Therefore, the design effect is high at 5.3, calculated as follows: $1 + ((\text{average cluster size } 16.4 - 1) * (1 + (\text{COV } 0.80^2)) * \text{ICC } 0.15)$.

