- *Outcome indicator*: The value for the outcome, ‘appropriate clinical actions for complications’, is unknown and thus 50% gives the most conservative estimate for the facilities in the control group using the paper partographs.
- *Effect size*: We expect a 30% point improvement on this indicator in facilities using ePartogram, the intervention sites, to 80%.

Adjusted for design effect, the total number of partographs or ePartograms needed are 1004 per study group, or 2009 in both groups. Due to the fact that there may be additional changes to facility selection, this number of partographs to review may increase somewhat based on the formulas. So we request the number of partographs to review to be up to **2,200 in total** .

Table 1. Sample Size Calculation Parameters

Table 1. Sample size scenarios for ePartogram effectiveness study

Availability of partographs in selected sites per month	536.8	Proportion of all births that have a partograph filled out	80%	671	1342	All 12 facilities - births monthly
Cluster size (Average) (formula based on 3 cells)	17.0					
Intra-class correlation coefficient (ICC)	0.15					
Number of clusters (facilities) PER ARM	6	(total 12 facilities in both study arms)				
Proportion of women whose labor crosses the Action line (a)	19%		Design effect (formula based on cells)	5.3		
Coefficient of variation (determined from number)	90%					
Effective Size: Detecting difference between arms on main indicator: "Case is appropriately managed"	Comparison group	ePartogram group	Unadjusted sample size (in a simple random sample) to detect difference	Adjusted for design effect	Total no of partographs required per arm	Total no of partographs or ePartograms: both study arms
	50%	70%	90	482	2536	5071
	50%	75%	55	293	1543	3087
	50%	80%	36	191	1004	2009

Sample size for qualitative interviewing

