Intrapartum death (fresh stillbirth rate) (Tool 5)	Number of fresh stillbirths. This is a count variable.	All live births	Same as above.
Adverse perinatal events (Neonatal deaths <24 hours+ intrapartum death (fresh stillbirth rate))	Number of neonatal deaths and fresh stillbirths	All live births	Same as above.

Statistical analysis plan

Outcomes will be dichotomous, yes/no for each measure.

In the main statistical analysis of our primary outcomes, we will focus on program effect (intervention (ePartogram) group of facilities versus comparison (paper program) group of facilities) as the main predictor of interest. The analysis will be performed at the level of the individual case (partogram). In preliminary analyses we will conduct univariable and bivariable analyses to assess the distribution of key variables and joint distributions and unadjusted relationships.

In final analyses addressing study aims, we will fit multi-level, multivariable regressions models for the outcomes with adjustment for possible confounders and account for clustering by provider and/or study clinic by the use of GEE.

While we have selected clinics roughly matched between the intervention and comparison regions, we will still evaluate confounding to attain the least biased estimate of our intervention effect. Facility level possible confounders are: monthly case load of laboring women, number of providers, key equipment availability etc. Provider-level possible confounders that may be adjusted for are years of work experience since graduation and cadre. Woman-level possible confounders are age and parity.

5. Describe whether you are collecting or storing **personal identifiers**, and if yes, why you need them, and when and how you plan to dispose of them. Signatures on consent forms are considered to be identifiers.

Identifiers of Providers

Our study will assign each facility and each provider a study id number of the Health Worker Line Listing form to be updated monthly. This will be kept separately from partograph data.

partograph review analysis: the paper partograph has a place for a provider to sign it. When we scan/photocopy paper partographs, we will obscure the provider name (cover with lose paper) but will we add/write on it the provider study id number.

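### The 1004 charts per group is solved with normal quantiles and a design effect for 17 cases per facility; with 6 against 6 facilities it gives about 48% power on the plan's own inputs

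*Combined protocol and SAP*

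**What the plan says.** Section III.B sizes the study on the third primary question (P3), appropriate clinical action for complications. For the control value it says that "50% gives the most conservative estimate for the facilities in the control group using the paper partographs", and it expects 80% in the ePartogram facilities. On sites it says "The available 12 sites (6 in each study arm) have 1342 births per month", and on coverage "We believe 80% of these will have a partograph completed during the study". It takes 19% of labors as complicated, an ICC of 0.15, a coefficient of variation (COV) of 90% and a design effect of 5.3.

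Table 1 starts from a column headed "Unadjusted sample size (in a simple random sample) to detect difference" (90, 55 and 36 for targets of 70%, 75% and 80%). It multiplies by the design effect and converts complicated cases to charts. The 80% row gives the stated requirement: "Adjusted for design effect, the total number of partographs or ePartograms needed are 1004 per study group, or 2009 in both groups". III.B then asks for up to 2,200 charts in total.

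On allocation, III.A (Phases, item 2) says: "Within each region, equal numbers of facilities that will be purposively assigned to the study groups". On analysis, the statistical analysis plan in V.C.4 says the models will "account for clustering by provider and/or study clinic by the use of GEE". Neither place makes an allowance for there being only 12 facilities, and III.B prints no alpha and no power.

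**The concern.** A design effect enlarges the variance. It does not change the reference distribution: the formula still uses 1.96 and 0.84, as if there were very many independent units. Here the arm is a property of the facility and there are 12 facilities. A two-group comparison that holds its 5% level has at most 2 × 6 − 2 = 10 degrees of freedom, with a critical value of 2.23.

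The design effect must also match the cluster size that the final total implies. With the number of facilities fixed, more charts mean larger clusters and therefore a larger design effect. Table 1 holds it at one value for all three rows.

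P3 is the question that sized the study, and the results are meant to inform the Ministry of Health on wider use. A null P3 result read as coming from a study of adequate size would count as stronger evidence against the ePartogram than it is.

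**Working it through.** **Inputs.** From III.B and Table 1: 6 facilities per arm; 536.8 charts per arm per month (671 × 0.80); 19% complicated; cluster size 17.0; ICC 0.15; COV 0.90; 50% against 80%. Assumed because not printed: two-sided 5% and 80% power, unpooled variance.

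**1. Reproduce the plan's figures.** n = (p1q1 + p2q2) × (1.96 + 0.84)² / (p2 − p1)²:
- 70%: 0.46 × 7.84 / 0.04 = 90.2
- 75%: 0.4375 × 7.84 / 0.0625 = 54.9
- 80%: 0.41 × 7.84 / 0.09 = 35.7

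These match 90, 55 and 36. For the 80% row, a pooled variance gives 39, a continuity correction 45, 90% power 52 and a one-sided test 31, so none of these was used.

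Cluster size: 536.8 × 0.19 / 6 = 17.0, which is one month of complicated cases per facility. Design effect: 1 + (17.0 − 1) × (1 + 0.90²) × 0.15 = 5.34. Then 35.7 × 5.34 ≈ 190.9 cases, and 190.9 / 0.19 ≈ 1004 charts per arm, 2009 in total. The table is reproduced.

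**2. Change only the reference distribution.** At 1004 per arm there are 1004 × 0.19 = 190.8 cases. Effective size is 190.8 / 5.34 = 35.7, and noncentrality is 0.30 / √(0.41 / 35.7) = 2.80. Power is 80% by z, 71% by noncentral t with 10 df, and 70% with 9 df (region in the model).

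**3. Match the design effect to the stated total.** 190.8 / 6 = 31.8 cases per facility, not 17.0. This is 1004 / 536.8 = 1.87 months of charts, in keeping with the 2 or 3 months of collection expected in V.C.3. The plan's formula gives 1 + 30.8 × 1.81 × 0.15 = 9.36. Effective size is 190.8 / 9.36 = 20.4, and noncentrality is 0.30 / √(0.41 / 20.4) = 2.12. Power is 56% by z and **48%** with 10 df (47% with 9 df).

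**4. The ceiling and larger totals** (50% against 80%, 10 df):

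| Total charts | Cases per facility | Design effect | Effective size per arm | Power |
|---|---|---|---|---|
| 2,008 (1004 per arm) | 31.8 | 9.36 | 20.4 | 48% |
| 2,200 | 34.8 | 10.19 | 20.5 | 48% |
| 2,480 | 39.3 | 11.39 | 20.7 | 49% |

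As cases per facility grow, effective size per arm tends to 6 / (0.15 × 1.81) = 22.1, below the 35.7 needed. Noncentrality is then 0.30 / √(0.41 / 22.1) = 2.20, so power is capped near 51% with 10 df (60% by z).

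**5. Detectable value.** With 10 df, 80% power needs a noncentrality of about 3.11. At effective size 20.4, a value of 90% gives 0.40 / √(0.34 / 20.4) = 3.10. The detectable value is therefore about 90% against 50%.

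**6. The other two rows, treated the same way.**
- 75% row: 1543 × 0.19 / 6 = 48.9 cases per facility, design effect 13.99, effective size 20.9, noncentrality 0.25 / √(0.4375 / 20.9) = 1.73, power about 35%.
- 70% row: 2536 × 0.19 / 6 = 80.3 cases per facility, design effect 22.53, effective size 21.4, noncentrality 0.20 / √(0.46 / 21.4) = 1.36, power about 23%.

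**7. Sensitivity.** III.B also prints a COV of 0.80 inside its formula. With 0.80 at 31.8 cases per facility, the design effect is 8.58 and power 51% with 10 df.

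**The case against.** - **The sum is right.** Table 1 reproduces, so a reader who infers an arithmetic slip would be wrong. Nor does the plan ignore clustering: only the 36 is an individual-level figure, and the 1004 already carries an inflation of 5.34. The fault is one of method: normal quantiles, and a design effect at the wrong cluster size. This stands.
- **Alpha and power are not stated.** True. A reader might infer that the plan promises 80% power; no passage says so. The values rest on reproducing all three rows, while the pooled, continuity-corrected, 90%-power and one-sided alternatives tried do not return 36.
- **The 10 df depends on the test.** V.C.4 plans case-level GEE without naming a small-sample correction. A reader might infer that the analysis as written would reject only 48% of the time. The documents do not support that: uncorrected GEE with 12 clusters would tend to show the problem as excess type I error instead. Power is meaningful only for a test that holds its level, and for such a test 10 df is the most available. The facility-level covariates that V.C.4 allows would reduce it (8 df gives 69% at the printed design effect).
- **Only the t step matters, so 71% is the answer and about 2,480 charts would restore 80%.** This is tempting but fails on the plan's own inputs. Both figures keep 5.34 while the total implies 31.8 or more cases per facility. At 2,480 charts power is 49%.

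**Conclusion.** The concern holds. The figure given as needed, 1004 per group, does not deliver the power its formula was solved for. At the printed design effect the small number of facilities alone brings 80% down to about 71%, which is an upper figure. With the design effect the stated total implies, power for 50% against 80% is about 48%. It is about the same at 2,200 charts and is capped near 51% for 12 facilities.

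This rests on the inferred two-sided 5% and 80%, on Table 1's ICC of 0.15 and COV of 0.90, on 19% complicated labors, and on a test with 10 df. The ICC is the plan's assumption, not an estimate from these sites; a lower value would raise both the power and the cap. The result concerns P3 only. It does not show that the study is uninformative on P1 or P2, which use other denominators and were not the basis of the size.

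**What to change.** In III.B and Table 1, keep the 12 facilities and the 2,200 ceiling, and:

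- print the alpha, sidedness and power used;
- recalculate all three rows with t quantiles on 10 df (9 if region is in the model) and a design effect computed at the cluster size each stated total implies;
- since no chart total reaches 80% power on any row with 6 facilities per arm at these inputs, report power for each row in place of a required size;
- state what the design delivers: about 48% power for 50% against 80%, or a detectable value of about 90% against 50% at 80% power;
- use one cluster size and one COV throughout (the text has 17.6, 16.4 and 0.80 where Table 1 has 17.0 and 0.90; the formula as printed, with 16.4 and 0.80, gives 4.79, not 5.3);
- if 71% is shown, label it as conditional on the printed design effect of 5.34.

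The cost is a rewording of III.B and a recalculated table, with no extra charts or sites. The downside is that the stated figures become less favourable.

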⁴ SBA: According to the WHO, a skilled birth attendant is a doctor, nurse or midwife “trained to proficiency in the skills needed to manage normal (uncomplicated) pregnancies, childbirth and the immediate postnatal period, and in the identification, management and referral of complications in women and newborns”. (“Making pregnancy safe: the critical role of the skilled birth attendant” – joint statement by WHO, ICM, FIGO [http://apps.who.int/iris/bitstream/10665/42955/1/9241591692.pdf\(\)](http://apps.who.int/iris/bitstream/10665/42955/1/9241591692.pdf)

We are including providers regardless of number of years in maternity ward because seasoned providers could have practices that are not consistent with labor management standards and newly trained providers may be practicing exactly according to labor management standards after their pre-service training.

At each site, we will collect the register data (via photograph or scan). Analysis of this data and data capture will be mentioned in the information sheet and agreement with the facility in-charge.

We plan to capture data from on all partographs in both study groups and analyze all partographs that are started or filled out on clients in both study groups.

Women/Clients

Women in labor will receive the recommended care according to the standard-of-care guidelines in both study groups. Women's interactions with providers will follow normal guidelines. The difference is that the intervention group facility providers will use the ePartogram instead of the paper partograph to document measurements. The ePartogram is operating as expected. Back-up paper partographs will be available at each site. Additionally, data that we analyze will not have women's names or identifiers. As such, we will not consent women clients to our study.

Qualitative interviews with in-charges and district authorities.

Inclusion criteria: supervise providers (or in-charges) who used the ePartogram or paper partograph to record care to at least 3 clients OR who supervise providers who have done this. OR facility administrators who supervise the in-charges or department heads

Providers – for qualitative data.

Qualitative Interviews will begin in the second month after the providers have had time to use the ePartogram or partograph following the training at the beginning.

Inclusion criteria: used the ePartogram or paper partograph to record care to at least 3 clients.

V. Study Procedures

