
P1. Compliance with globally-recommended labor monitoring practices and recording on the partograph of the information obtained – complete on admission (Tool 4)
	
We will examine each parameter and enter to the database.
 
Overall, this will be marked ‘yes’ if 11 of the 12 items (all except urine volume) are measured at admission (fetal heart rate, cervical dilation, systolic and diastolic blood pressure, amniotic fluid, moulding, head descent, contractions, pulse, temperature, urine protein, acetone and volume); and otherwise ‘no’. Binary variable.
	
All labors with partograph or ePartogram
 
Unit of analysis is each case (partograph).
	
First, we will examine the frequency/prevalence of each measurement recorded on admission and compare between the two study groups
 
Second, We will examine the percent of cases marked ‘yes’ (defined at left). Independent variable is study group. Bivariate analysis will be an unadjusted logistic regression accounting for clustering in the facility or in the provider. In multivariable analysis, other control factors added may be facility type, client volume, region or provider variables.

- Complete over entire labor (Tool 4)
	
We will examine each parameter and enter to the database. Then we will see how many hours was the labor for the appropriate frequency, per the Jhpiego Clinical Rules and determine whether this was done to a large extent on time.
 
Overall, this will be marked ‘yes’ if 11 of the 12 items (all except urine volume) are measured in first 4-hour period at the specified intervals (reviewer will determine for each item if occurred within the interval): fetal heart rate every 30 min, cervical
	
All labors with partograph or ePartogram
	
Same as above – except it will be for the first four hour period

	dilation every 4 hours, systolic and diastolic blood pressure every 4 hours, amniotic fluid if membranes rupture, moulding when present head descent every 2 hours, contractions every 30 min, pulse every 30 min, temperature every 2 hours, urine protein, acetone and volume, all at every 4 hours. ; and otherwise ‘no’. Binary variable.		
- Complete over entire labor for a subset of women who arrived at 4 or 5 cm			

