ePartogram will enter the provider's study id number. There will be a drop-down menu in which the provider name and study id appears, but only provider study id will end up in the back-end database. There will be no names kept in the database of ePartogram information.

Each time the study staff visits the facility, the health worker line listing forms and database will be updated with names of new providers added to the study and for intervention sites only, who pass the post-training test for ePartogram

Written consent forms will be kept for 3 years after the study date of closing with IRB.

- a. *register review analysis:* The register has a field for provider name. Prior to our taking scan/photo of registers, we will obscure the provider name and replace the provider name with the provider study id from the Health Worker Line Listing.

Identifiers of Women

- a. *partograph review analysis:* The name of the client/woman is on the partograph. Prior to photographing partographs, we will make sure the partograph has the woman's 'hospital admission number'. We will verify that this is the same as recorded in the register. Once the admission number is verified, then we will scan/photocopy the partograph and obscure the woman's name by covering with a small piece of paper prior to scanning the partograph.
- b. When a new client sheet is started in the ePartogram, the software will automatically assign a study-generated ID number to each laboring woman's eParotgram record. This record will also have the woman's name during the care process, for printing the ePartogram record to leave at the facility. The study ID will be the facility number (i.e. MER01 for the first facility in Meru) + date + 01 for the first woman admitted in labor.
- c. *register review analysis:* The register has a field for woman's name. When we scan/photocopy the register, we can obscure women's names.

Identifiers of Providers - for Qualitative Interviews.

We may temporarily keep track of provider and supervisors names only for the purpose of setting up an interview at a convenient time. However, no names or identifiers will be collected or recorded on qualitative participants.

The names of providers receiving any payment or reimbursement as described in the consent form will be retained for financial purposes only in secure financial database at Jhpiego.

6. Answer the following if they are relevant to your study design:

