Providers in control sites will monitor women in labor using the standard-of-care partograph. In the intervention arm, providers will use the ePartogram, an electronic version of the partograph.

- Will you use a **placebo or non-treatment group**, and is that justifiable?

Please see prior question. We plan to study the effectiveness of the ePartogram in improving labor management outcomes, which currently is unknown.

- Explain when you may **remove a participant** from the study.

All birth attendants at selected sites who meet eligibility requirements will be included and not removed unless they are transferred away from these sites.

A provider in the ePartogram facility may choose not to use the tablet and instead use the paper partograph to monitor clients, this is a voluntary choice. Or, if an ePartogram tablet is temporarily not working, the provider will use a paper partograph for labor monitoring. Paper partographs will be available at all study sites. Paper partographs used at ePartogram sites will nonetheless contribute to the data from the Intervention sites, for 'intention to treat' analysis. We will monitor this situation if this arises.

- What happens to participants on study intervention when the **study ends?**

After the study, the ePartogram facilities will return to having providers use the standard-of-care paper partograph for labor management.

- Describe the process for **referring participants** to care outside the study, if needed.

The regular referral processes currently in place at each facility will be described at the start of the study and the same procedures will apply during our study.

VI. Data Custody, Security, and Confidentiality Protections

The sections below describe types of data sources and how they will be protected. For the type(s) of data, put an "X" in the appropriate box to the left of the section that best describes how you will minimize the risk of a breach of confidentiality for your study. Note, as appropriate, how you will record/store data. These descriptions represent MINIMAL measures; you may add more stringent protections and other relevant information in B.

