The ePartogram has the potential to improve appropriate use of the partograph and ultimately to improve intrapartum maternal and fetal outcomes. If this study demonstrates ePartogram effectiveness in a clinical setting, it could contribute to efforts to make the ePartogram available widely in resource-challenged settings.

IX. Payment:

- A. Describe the form, amount, and schedule of payment to participants. Reimbursement for travel or other expenses is not “payment,” and if the study will reimburse, explain.
- We tell providers in consent script: “As a SBA, you will receive a per diem of 1750 Kenyan Shillings for each day that you take part in the training workshop. You will also receive 2000 Kenyan Shillings transportation allowance for each round trip to the training site.
- Accommodation and lunch will be provided for the duration of the training.
- If you are selected for and complete the interview, you will receive an additional 500 Kenyan Shillings for your time.”

B. Include the possible total remuneration and any consequences for not completing all phases of the research.

SBAs would receive a maximum of 10750 Kenyan Shillings (~ US\$108) remuneration comprised of 1750 Kenyan Shillings per diem for each of five training days and 2000 Kenyan Shillings for roundtrip ground transportation to the training. Accommodation and lunch will be provided during the trainings. An additional 500 Shillings will be offered to participants completing a qualitative interview; providers can participate in a maximum of 2 qualitative interviews. There are no consequences for providers if they choose to withdraw or not participate in the study at any time.

Facility records management staff person or, in the absence of such a person, the nurse in-charge selected to scan partograph data at the control sites and to photograph maternity registers will receive 2000 Kenyan Shillings (~US\$20) per day worked. Nurse in-charges will work at most 2 hours per day for 5 days in a week, equivalent to 1 day worked per week. Study implementation will take up to 3 months (or 12 weeks). The possible total remuneration for a nurse in-charge is 24,000 Kenyan Shillings (~ US\$240).

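### P1 is analyzed only among labors that have a chart, the ePartogram can change which labors get one, and no between-arm comparison of chart coverage is planned

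*Combined protocol and SAP*

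**What the plan says.** Research question P1 (Section I) compares facilities: do those using the ePartogram comply better with recommended labor monitoring and its recording? Table 5 then defines the P1 cases, both on admission and over labor, as "All labors with partograph or ePartogram". The unit is the individual chart, and the statistical analysis plan below Table 5 repeats that analysis is at case level. Section IV (Providers) says the study will "analyze all partographs that are started or filled out on clients in both study groups".

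Four other statements bear on coverage:

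- Section III.B gives 671 births per month for six facilities and adds: "We believe 80% of these will have a partograph completed during the study".
- Section II describes routine paper use in low- and middle-income countries as low and uneven. It presents the ePartogram as a way to raise timely use.
- Section III.A, phase 1, lists coverage over the previous three months as an item of the formative assessment. Section V.C.3 mentions coverage during the study only as something that affects how long data collection takes.
- Section V.C.6.f says: "Paper partographs used at ePartogram sites will nonetheless contribute to the data from the Intervention sites, for 'intention to treat' analysis".

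Coverage is not an outcome in Table 5, and the statistical analysis plan does not compare it between arms.

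**The concern.** A labor with no chart has no recorded monitoring, which is the plainest failure of recording that P1 could register, yet it drops out of the comparison. That would matter less if coverage were outside the intervention's reach. Here it is part of what the tool is meant to improve. It could also fall, since Table 7 names tablet or software failure and discomfort with several clients at once as risks.

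Selecting the analysis set on something the intervention can change allows error in either direction. An arm that charts fewer labors but charts them well looks better than it is. An arm in which the tool brings in labors that would otherwise have gone uncharted can look worse than it is, if those extra charts are less complete. P1 is a primary question, and Section I says the study will inform the Ministry of Health on whether to use the tool more widely.

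**Working it through.** **Inputs from the documents.** Births per arm per month: 671 (Section III.B). Expected coverage: 80% of births with a completed chart, one figure for both arms (Section III.B, Table 1). Completeness: 58%, from the Kenyan survey quoted in Section II.

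**The plan's own figure.** 671 × 0.80 = 536.8 charts per arm per month, which matches Table 1. The remainder is 671 − 536.8 = 134.2 births per arm per month without a completed chart. This is an upper guide to what P1 omits, because P1 also keeps charts that were started but not completed, and births include some that would not need a chart.

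**Formula.** Let c be coverage and q the proportion complete among charts. If an uncharted labor counts as not compliant, compliance per birth is c × q. The planned P1 difference is q1 − q0. The per-birth difference is c1·q1 − c0·q0, which becomes q(c1 − c0) when q is equal in the two arms.

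**Illustration.** Coverage by arm and the 68% are assumptions.

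| Coverage, control / ePartogram | Per birth, q = 58% in both | Difference (P1 shows 0) | Per birth, q = 58% / 68% | Difference (P1 shows +10) |
|---|---|---|---|---|
| 70% / 90% | 40.6% vs 52.2% | +11.6 | 40.6% vs 61.2% | +20.6 |
| 75% / 85% | 43.5% vs 49.3% | +5.8 | 43.5% vs 57.8% | +14.3 |
| 80% / 80% | 46.4% vs 46.4% | 0 | 46.4% vs 54.4% | +8.0 |
| 85% / 75% | 49.3% vs 43.5% | −5.8 | 49.3% vs 51.0% | +1.7 |
| 90% / 70% | 52.2% vs 40.6% | −11.6 | 52.2% vs 47.6% | −4.6 |

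With q = 58% in both arms, each 10 points of coverage gap is worth 5.8 points per birth.

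**Understatement, limiting case.** Suppose control charts 80 of 100 labors with 58% complete: 80 × 0.58 = 46.4 compliant labors. Suppose the ePartogram arm has the same 46.4 plus 10 extra charts, none complete. P1 then shows 46.4/90 = 51.6% against 58%, a deficit of 6.4 points, although compliant labors per 100 births are equal.

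**Sensitivity to the 58%.** The survey sentence does not make clear whether 58% is of charts or of all cases. If it is of all cases, with a partograph used in 88%, completeness among charts is 58/88 = 65.9%, and a 20-point coverage gap is worth 0.20 × 65.9 = 13.2 points. The survey item is also completion of every component, which is stricter than P1's rule of 11 of 12 items.

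**The case against.** The strongest reply is that quality of charting, given a chart, is a coherent target. P1 includes recording on the partograph, and a missing chart does not prove that monitoring was absent. Uncharted births include caesareans and perhaps late arrivals. Phase 2 of Section III.A fixes two referral-type hospitals in the intervention arm; if they have more such births, counting every uncharted delivery as a failure would penalize that arm mechanically. Table 7 expects tablet or software failure in under 5% of cases, with backup tablets and paper forms on site. All of this stands. It is why the planned P1 should be kept and the all-deliveries version used only as a sensitivity analysis. It does not supply the missing coverage comparison.

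A reader might also infer four stronger points that the documents do not support.

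- *That the plan contradicts its own intention-to-treat statement.* The phrase in Section V.C.6.f covers only paper charts used at ePartogram sites. The plan nowhere claims to analyze every labor, so this is a gap and not a contradiction.
- *That a coverage difference cannot be seen.* Tool 5 (Table 4) records deliveries by facility, and Section X.D counts them every two weeks. Coverage can be derived; what is missing is a plan to report it.
- *That backup paper forms at ePartogram sites will be missed.* Section IX.B does describe paying staff "selected to scan partograph data at the control sites and to photograph maternity registers", and phase 8 places daily scanning under control sites. But Section IV (Providers) and Section V.C.1(g) provide for capturing these forms, and Section V.C.2 describes scanning without limiting it to one arm. At most the wording needs aligning.
- *That 20% of eligible labors are lost.* The 80% refers to all births and to completed charts.

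**Conclusion.** The point holds in this form: P1 conditions on the existence of a chart, the intervention can affect that, and no between-arm comparison of coverage is planned. Read as the effect on facility-level compliance, P1 could therefore err in either direction.

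The size cannot be estimated from the documents, because they give no coverage by arm. The differences of −11.6 to +11.6 points at equal completeness are illustrations. They rest on assumed coverage of 70% to 90%, on the 58% survey figure applied to charts, and on counting uncharted labors as not compliant. If coverage proves similar in the two arms, the concern largely falls away, and the proposed report would show that. The change should be made, but the planned analysis need not be replaced.

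**What to change.** 1. Add partograph coverage to Table 5 as a reported outcome: charts started (paper or electronic) divided by register deliveries, by facility and arm, with a between-arm comparison that accounts for clustering by facility. Use the same calendar window for charts and deliveries. State how women referred out in labor are handled, since they may have a chart but no delivery at that site; Tool 5 counts referrals. Show the pre-study coverage from the formative assessment alongside.
2. Keep P1 as planned. Add a facility-level sensitivity analysis with register deliveries as denominator, counting uncharted labors as not compliant. Exclude deliveries not eligible for a chart, such as planned caesareans or late arrivals, where the register identifies them.
3. Align phase 8 and Section IX.B with Sections V.C.1 and V.C.2 on who scans paper charts at ePartogram sites.

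The cost is small: Tool 5 counts are already collected, and step 1 needs no individual matching. If matching is wanted, Section V.C.5 says of the partograph admission number: "We will verify that this is the same as recorded in the register". That check is described for partographs, while ePartogram records receive a software-generated ID.

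The downside is that eligibility may be only partly identifiable. Tool 5 as listed counts cesarean births without separating planned ones, and case mix may differ between arms. The facility-level version also cannot carry the provider and woman covariates of the case-level models. Both analyses should therefore be shown together.
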